Neurosensory	Mild impairment in sensation (decreased sensation, e.g., vibratory, pinprick, hot/cold in great toes) in focal area or symmetrical distribution; or change in taste, smell, vision, and/or hearing	Moderate impairment (moderately decreased sensation, e.g., vibratory, pinprick, hot/cold to ankles) and/or joint position or mild impairment that is not symmetrical	Severe impairment (decreased or loss of sensation to knees or wrists) or loss of sensation of at least moderate degree in multiple different body areas (i.e., upper and lower extremities)	Sensory loss involves limbs and trunk; paralysis; or seizures

MUSCULOSKELETAL				
	Grade 1	Grade 2	Grade 3	Grade 4
Arthralgia (joint pain)	Mild pain not interfering with function	Moderate pain, analgesics and/or pain interfering with function but not with ADL	Severe pain; pain and/or analgesics interfering with ADL	Disabling pain
Arthritis	Mild pain with inflammation, erythema or joint swelling, but not interfering with function	Moderate pain with inflammation, erythema or joint swelling; interfering with function but not with ADL	Severe pain with inflammation, erythema or joint swelling, and interfering with ADL	Permanent and/or disabling joint destruction
Myalgia	Myalgia with no limitation of activity	Muscle tenderness (at other than injection site) or with moderate impairment of activity	Severe muscle tenderness with marked impairment of activity	Frank myonecrosis

ADL=activities of daily living.

SKIN				
	Grade 1	Grade 2	Grade 3	Grade 4
Mucocutaneous	Erythema; pruritus	Diffuse, maculo-papular rash, dry desquamation	Vesiculation or moist desquamation or ulceration	Exfoliative dermatitis, mucous membrane involvement or erythema, multiforme or suspected Stevens-Johnson or necrosis requiring surgery
Induration	<15 mm	15 to 30 mm	>30 mm	N/A
Erythema	<15 mm	15 to 30 mm	>30 mm	N/A
Edema	<15 mm	15 to 30 mm	>30 mm	N/A
Rash at injection site	<15 mm	15 to 30 mm	>30 mm	N/A
Pruritus	Slight itching at injection site	Moderate itching at injection extremity	Itching over entire body	N/A

N/A=not applicable.

SYSTEMIC				
	Grade 1	Grade 2	Grade 3	Grade 4
Allergic reaction	Pruritus without rash	Localized urticarial	Generalized urticarial; angioedema	Anaphylaxis
Headache	Mild, no treatment required	Transient, moderate; treatment required	Severe; responds to initial narcotic therapy	Intractable; requires repeated narcotic therapy
Fever: oral	37.7 to 38.5°C or 100.0 to 101.5°F	38.6 to 39.5°C or 101.6 to 102.9°F	39.6 to 40.5°C or 103 to 105°F	>40°C or >105°F
Fatigue	Normal activity reduced <48 hours	Normal activity decreased 25 to 50%; >48 hours	Normal activity decreased >50%; cannot work	Unable to care for self

12.6. Appendix 6: Contraceptive Guidance and Collection of Pregnancy Information

Definitions

Woman of Childbearing Potential (WOCBP)

A woman is considered fertile following menarche and until becoming post-menopausal unless permanently sterile (see below)

Women in the following categories are not considered WOCBP

1. Premenarchal
2. Premenopausal female with ONE of the following:
 - Documented hysterectomy
 - Documented bilateral salpingectomy
 - Documented bilateral oophorectomy

Note: Documentation can come from the site personnel's: review of participant's medical records, medical examination, or medical history interview.

3. Postmenopausal female
 - A postmenopausal state is defined as no menses for 12 months without an alternative medical cause. A high follicle stimulating hormone (FSH) level in the postmenopausal range may be used to confirm a postmenopausal state in women not using hormonal contraception or hormonal replacement therapy (HRT). However, in the absence of 12 months of amenorrhea, a single FSH measurement is insufficient.
 - Females on HRT and whose menopausal status is in doubt will be required to use one of the non-hormonal highly effective contraception methods if they wish to continue their HRT during the study. Otherwise, they must discontinue HRT to allow confirmation of postmenopausal status before study enrollment.

Contraception Guidance

Female participants

Female participants of childbearing potential are eligible to participate if they agree to use a highly effective method of contraception consistently and correctly as described in [Table 8](#) in addition to using a male condom during intercourse.

Table 8 Highly Effective Contraceptive Methods

Highly Effective Contraceptive Methods That Are User Dependent^a Failure rate of <1% per year when used consistently and correctly.

Combined (estrogen- and progestogen-containing) hormonal contraception associated with inhibition of ovulation^b
 
 • oral • intravaginal • transdermal

Progestogen-only hormonal contraception associated with inhibition of ovulation^b
 
 • injectable

Highly Effective Methods That Are User Independent

 • Implantable progestogen-only hormonal contraception associated with inhibition of ovulation^b • Intrauterine device (IUD) • Intrauterine hormone-releasing system (IUS) • bilateral tubal occlusion

Vasectomized partner
 
(A vasectomized partner is a highly effective contraception method provided that the partner is the sole male sexual partner of the WOCBP and the absence of sperm has been confirmed. If not, an additional highly effective method of contraception should be used.)

Sexual abstinence
 
(Sexual abstinence is considered a highly effective method only if defined as refraining from heterosexual intercourse during the entire period of risk associated with the study drug. The reliability of sexual abstinence needs to be evaluated in relation to the duration of the study and the preferred and usual lifestyle of the participant.)

WOCBP=woman of childbearing potential.

- a. Typical use failure rates may differ from those when used consistently and correctly. Use should be consistent with local regulations regarding the use of contraceptive methods for participants in clinical studies.
- b. Hormonal contraception may be susceptible to interaction with the study drug, which may reduce the efficacy of the contraceptive method. In this case 2 highly effective methods of contraception should be utilized during the treatment period and through the Test-of-Cure (Day 10 to 13) Visit.

Pregnancy Testing

- WOCBP should only be included after a confirmed menstrual period and a negative highly sensitive urine pregnancy test
- Additional pregnancy testing will be performed on Day 5 and at the Test-of-Cure (Day 10 to 13) Visit, 5 to 8 days after the last dose of study treatment and as required locally
- Pregnancy testing will be performed whenever a menstrual cycle is missed or when pregnancy is otherwise suspected
- Pregnancy testing, with a sensitivity of 25 mIU/mL, will be performed using the test kit provided by the designated laboratory

Collection of Pregnancy Information

Female Participants who become pregnant

- Investigator will collect pregnancy information on any female participant, who becomes pregnant while participating in this study.
- Information will be recorded on the appropriate form and submitted to GlaxoSmithKline (GSK)/PPD within 24 hours of learning of a participant's pregnancy.
- Participant will be followed to determine the outcome of the pregnancy. The investigator will collect follow up information on participant and neonate, which will be forwarded to GSK. Generally, follow-up will not be required for longer than 6 to 8 weeks beyond the estimated delivery date.
- Any termination of pregnancy will be reported, regardless of fetal status (presence or absence of anomalies) or indication for procedure.
- While pregnancy itself is not considered to be an AE or SAE, any pregnancy complication or elective termination of a pregnancy will be reported as an AE or SAE.
- A spontaneous abortion is always considered to be an SAE and will be reported as such.
- Any SAE occurring as a result of a post-study pregnancy which is considered reasonably related to the study treatment by the investigator, will be reported to GSK as described in [Appendix 4](#). While the investigator is not obligated to actively seek this information in former study participants, he or she may learn of an SAE through spontaneous reporting.
- Any female participant who becomes pregnant while participating will discontinue study treatment.

12.7. Appendix 7: Genetics

USE/ANALYSIS OF DNA

- Genetic variation may impact a participant's response to therapy, susceptibility, severity, and progression of disease. Variable response to therapy may be due to genetic determinants that impact drug absorption, distribution, metabolism, and excretion; mechanism of action of the drug; disease etiology; and/or molecular subtype of the disease being treated. Therefore, where local regulations and institutional review board allow, a blood sample will be collected for DNA analysis.
- DNA samples will be used for research related to gepotidacin or uncomplicated urinary tract infections and related diseases. They may also be used to develop tests/assays (including diagnostic tests) related to and uncomplicated urinary tract infections. Genetic research may consist of the analysis of 1 or more candidate genes or the analysis of genetic markers throughout the genome [or analysis of the entire genome] (as appropriate)
- DNA samples will be analyzed if it is hypothesized that this may help further understand the clinical data.
- The samples may be analyzed as part of a multi-study assessment of genetic factors involved in the response to gepotidacin or study treatments of this class. The results of genetic analyses may be reported in the clinical study report or in a separate study summary.
- The sponsor will store the DNA samples in a secure storage space with adequate measures to protect confidentiality.
- The samples will be retained while research on gepotidacin (or study treatments of this class) or uncomplicated urinary tract infections continues but no longer than 15 years after the last participant last visit or other period as per local requirements.

12.8. Appendix 8: Liver Safety: Required Actions and Follow-up Assessments

Phase IIa liver chemistry stopping and increased monitoring criteria have been designed to assure participant safety and evaluate liver event etiology.

Phase IIa liver chemistry stopping criteria and required follow-up assessments

Liver Chemistry Stopping Criteria	
ALT Absolute	ALT \geq 8 x ULN
ALT Increase	ALT \geq 5 x ULN but <8 x ULN persists for \geq 2 weeks ALT \geq 3 x ULN but <5 x ULN persists for \geq 4 weeks
Bilirubin^{a,b}	ALT \geq 3 x ULN and bilirubin \geq 2 x ULN (>35% direct bilirubin)
INR^b	ALT \geq 3 x ULN and INR >1.5, if INR measured
Cannot Monitor	ALT \geq 5 x ULN but <8 x ULN and cannot be monitored weekly for \geq 2 weeks ALT \geq 3 x ULN but <5 x ULN and cannot be monitored weekly for \geq 4 weeks
Symptomatic^c	ALT \geq 3 x ULN associated with symptoms (new or worsening) believed to be related to liver injury or hypersensitivity
Required Actions and Follow-up Assessments	
Actions	Follow-up Assessments

 Immediately discontinue study treatment Report the event to GSK/PPD within 24 hours Complete the liver event eCRF and complete an SAE data collection tool if the event also meets the criteria for an SAE^b Perform liver event follow-up assessments Monitor the participant until liver chemistries resolve, stabilize, or return to within baseline (see MONITORING below) Do not restart/rechallenge participant with study treatment If restart/rechallenge not allowed or not granted, permanently discontinue study treatment and continue participant in the 	
 Viral hepatitis serology^d Obtain INR and recheck with each liver chemistry assessment until the transaminases values show downward trend Only in those with underlying chronic hepatitis B at study entry (identified by positive hepatitis B surface antigen), quantitative hepatitis B DNA, and hepatitis delta antibody^e Obtain blood sample for PK analysis, within 24 hours after last dose^f Serum creatine phosphokinase and lactate dehydrogenase Fractionate bilirubin, if total bilirubin


study for any protocol-specified follow-up assessments
 
MONITORING:
 
For bilirubin or INR criteria:
 
 Repeat liver chemistries (include ALT, AST, alkaline phosphatase, bilirubin) and perform liver event follow-up assessments within 24 hours Monitor participants twice weekly until liver chemistries resolve, stabilize, or return to within baseline A specialist or hepatology consultation is recommended 
For All other criteria:
 
 Repeat liver chemistries (include ALT, AST, alkaline phosphatase, bilirubin) and perform liver event follow-up assessments within 24 to 72 hours Monitor participants weekly until liver chemistries resolve, stabilize, or return to within baseline 	
≥2 x ULN
 
 Obtain complete blood count with differential to assess eosinophilia Record the appearance or worsening of clinical symptoms of liver injury, or hypersensitivity, on the AE report form Record use of concomitant medications on the concomitant medications report form including acetaminophen, herbal remedies, other over the counter medications. Record alcohol use on the liver event alcohol intake eCRF page 
For bilirubin or INR criteria:
 
 Antinuclear antibody, antismooth muscle antibody, type 1 antiliver kidney microsomal antibodies, and quantitative total immunoglobulin G (IgG) or gamma globulins. Serum acetaminophen adduct HPLC assay (quantifies potential acetaminophen contribution to liver injury in participants with definite or likely acetaminophen use in the preceding week [James, 2009]). NOTE: not required in China Liver imaging (ultrasound, magnetic resonance, or computed tomography) and/or liver biopsy to evaluate liver disease: complete liver imaging and/or liver biopsy eCRFs.
--	--

AE=adverse event; ALT=alanine aminotransferase; AST=aspartate aminotransferase; eCRF=electronic case report form; GSK=GlaxoSmithKline; HPLC=high-performance liquid chromatography; IgM=immunoglobulin M; INR=international normalized ratio; PK=pharmacokinetic; SAE=serious adverse event; ULN=upper limit of normal.

- Serum bilirubin fractionation should be performed if testing is available. If serum bilirubin fractionation is not immediately available, discontinue study treatment for that participant if ALT ≥3 x ULN and bilirubin ≥2 x ULN. Additionally, if serum bilirubin fractionation testing is unavailable, record presence of detectable urinary bilirubin on dipstick, indicating direct bilirubin elevations and suggesting liver injury.
- All events of ALT ≥3 x ULN and bilirubin ≥2 x ULN (>35% direct bilirubin) or ALT ≥3 x ULN and INR>1.5, if INR measured which may indicate severe liver injury (possible 'Hy's Law'), must be reported as an SAE (excluding studies of hepatic impairment or cirrhosis); INR measurement is not required and the threshold value stated will not apply to participants receiving anticoagulants.

- c. New or worsening symptoms believed to be related to liver injury (such as fatigue, nausea, vomiting, right upper quadrant pain or tenderness, or jaundice) or believed to be related to hypersensitivity (such as fever, rash or eosinophilia).
- d. Includes: hepatitis A IgM antibody; hepatitis B surface antigen and hepatitis B core antibody (IgM); hepatitis C RNA; cytomegalovirus IgM antibody; Epstein-Barr viral capsid antigen IgM antibody (or if unavailable, obtain heterophile antibody or monospot testing); hepatitis E IgM antibody.
- e. If hepatitis delta antibody assay cannot be performed, it can be replaced with a polymerase chain reaction of hepatitis D RNA virus (where needed) [Le Gal, 2005].
- f. The PK sample may not be required for participants known to be receiving placebo or non-GSK comparator treatments. Record the date/time of the PK blood sample draw and the date/time of the last dose of study treatment prior to PK blood sample draw on the eCRF. If the date or time of the last dose is unclear, provide the participant's best approximation. If the date/time of the last dose cannot be approximated OR a PK sample cannot be collected in the time period indicated above, do not obtain a PK sample. Instructions for sample handling and shipping are in the Study Reference Manual.

Phase III liver chemistry increased monitoring criteria with continued therapy

Liver Chemistry Increased Monitoring Criteria – Liver Monitoring Event	
Criteria	Actions

ALT ≥ 5 x ULN and < 8 x ULN and bilirubin < 2 x ULN without symptoms believed to be related to liver injury or hypersensitivity, and who can be monitored weekly for 2 weeks.
 
OR
 
ALT ≥ 3 x ULN and < 5 x ULN and bilirubin < 2 x ULN without symptoms believed to be related to liver injury or hypersensitivity, and who can be monitored weekly for 4 weeks.
	
 • Notify the GSK/PPD medical monitor within 24 hours of learning of the abnormality to discuss participant safety. • Participant can continue study treatment • Participant must return weekly for repeat liver chemistries (ALT, AST, alkaline phosphatase, bilirubin) until they resolve, stabilize, or return to within baseline • If at any time participant meets the liver chemistry stopping criteria, proceed as described above • If ALT decreases from ALT ≥ 5 x ULN and < 8 x ULN to ≥ 3 x ULN but < 5 x ULN, continue to monitor liver chemistries weekly. • If, after 4 weeks of monitoring, ALT < 3 x ULN and bilirubin < 2 x ULN, monitor participants twice monthly until liver chemistries normalize or return to within baseline.

ALT=alanine aminotransferase; AST=aspartate aminotransferase; GSK=GlaxoSmithKline; ULN=upper limit of normal.

References

[figure not shown]

12.9. Appendix 9: Algorithm for the Microbiological Intent-to-Treat Population

Participants will be included in the Microbiological Intent-to-Treat Population if they receive at least 1 dose of gepotidacin and have a qualifying bacterial uropathogen (defined in Figure 4) at Baseline (predose on Day 1) from a quantitative bacteriology culture of a pretreatment clean-catch midstream urine specimen.

The algorithm for determining microbiological evaluable participants based on microbiology laboratory quantitative culture results is provided in Figure 4.

Figure 4 Baseline Algorithm for the Microbiological Intent-to-Treat Population

CFU=colony-forming units; micro-ITT=Microbiological Intent-to-Treat.

References

Chan WW. Chapter 3.12: Urine cultures. In: Leber AL, editor. Clinical microbiology procedures handbook, 4th ed. Vol 1-3. Washington, DC; ASM Press; 2016.

12.10. Appendix 10: Clinical Signs and Symptoms Scoring for Acute Cystitis

Acute cystitis clinical signs and symptoms will be scored as follows:

Clinical Signs and Symptoms	None	Mild	Moderate	Severe
	Participants' normal clinical presentation prior to current infection	Symptom is easily tolerated, causing minimal discomfort and not interfering with everyday activities	Symptom is sufficiently discomforting to interfere with normal everyday activities	Symptom prevents normal everyday activities
	SCORE 0	SCORE 1	SCORE 2	SCORE 3
Dysuria				
Frequency				
Urgency				
Lower abdominal or suprapubic pain				

Scores will be recorded by the investigator or a qualified designee. When possible, the same scorer will be used at all assessment time points.

1. INTRODUCTION

The purpose of this reporting and analysis plan (RAP) is to describe the analyses to be included in the Clinical Study Report for Protocol: 206899.

2. SUMMARY OF KEY PROTOCOL INFORMATION

This Phase IIa study is designed primarily to evaluate plasma and urine pharmacokinetics (PK) of gepotidacin in female participants with clinical signs and symptoms of acute cystitis. As this PK study will be conducted in female participants with clinical signs and symptoms of acute cystitis, exploratory clinical and microbiological efficacy of gepotidacin will also be assessed.

2.1. Changes to the Protocol Defined Statistical Analysis Plan

Changes from the originally planned statistical analysis specified in the protocol are outlined in [Table 1](#).

Table 1 Changes to Protocol Defined Analysis Plan

Protocol	Reporting & Analysis Plan	
Statistical Analysis Plan	Statistical Analysis Plan	Rationale for Changes

 Clinical outcome will be determined by the investigator 	
 In addition to investigator-determined clinical outcome, a sponsor-determined clinical outcome will be programmatically derived 	
 To solve the potential dilemma that a participant with record missing or unable-to-determine at Test-of-Cure (TOC) visit but free of signs and symptoms of acute cystitis at Follow-up Visit will likely be determined as “clinical success” by the investigator but falls under failure per US Food and Drug Administration (FDA) guidance [DHHS, May 2018; DHHS, June 2018].

 Clinical outcome will be determined at the On-Therapy (Days 2 through 5), TOC, and Follow-up visits by comparing the signs and symptoms of acute cystitis to those present at Baseline. Clinical response (success or failure) will be determined at the TOC and Follow-Up visits 	
 In addition, clinical cure, a binary result of ‘Yes’ or ‘No’ will be determined at the On-Therapy (Days 2 through 5), TOC, and Follow-Up visits. Clinical cure is defined as complete resolution of signs and symptoms of acute cystitis present at Baseline, with no new signs and symptoms, and no use of other antimicrobial therapy. Clinical cure at Follow-up visit must also meet clinical cure at TOC in addition to above criteria 	
 To apply a clinical criterion that is consistently focusing on complete resolution of clinical signs and symptoms through On-Therapy, TOC, and Follow-Up visits.

2.2. Study Objective(s) and Endpoint(s)

Objectives	Endpoints
Primary Objectives	Primary Endpoints

 To determine the plasma PK parameters of gepotidacin following repeat oral doses of gepotidacin (1500 mg [2 × 750-mg tablets] twice daily [BID] for 5 days) in adult female participants with acute cystitis 	
 Plasma gepotidacin area under the concentration-time curve (AUC) from zero (predose) over the dosing interval (AUC[0-τ]), maximum plasma concentration (C_{max}), and time of occurrence of C_{max} (t_{max}) on Days 1 and 4 and apparent steady state clearance (CL_{ss}/F) and accumulation ratio (R₀) on Day 4 Plasma predose concentration (C_τ) of gepotidacin on Days 1 through 5
Secondary Objectives	Secondary Endpoints

 To determine the urine PK parameters of gepotidacin following repeat oral doses of gepotidacin in adult female participants with acute cystitis 	
 Urine gepotidacin amount of drug excreted over 12 hours (A_e 12h), amount of drug excreted in urine in a time interval (A_e[t1-t2]), percentage of the given dose of drug excreted in urine (fe%), and renal clearance (CL_r) of gepotidacin on Days 1 and 4 Urine predose concentration (C_τ) on Days 1 through 5

 To assess the safety and tolerability of repeat oral doses of gepotidacin in adult female participants with acute cystitis 	
 Treatment-emergent adverse events (AEs) and serious AEs (SAEs) and change from baseline results for vital sign measurements, electrocardiograms (ECGs), and clinical laboratory tests
Exploratory Objectives	Exploratory Endpoints

 To explore the combined clinical and microbiological efficacy of gepotidacin in adult female participants with acute cystitis who have a qualifying baseline uropathogen 	
 Therapeutic response (combined per-participant microbiological and clinical response) at the TOC Visit

 To assess time to eradication of uropathogens in adult female participants with acute cystitis who have a qualifying baseline uropathogen 	
 Microbiological outcome on Days 2 through 5; Microbiological outcome and response at the TOC and Follow-up Visits

 To explore time to resolution of signs and symptoms in adult female participants with acute cystitis 	
 Investigator-determined clinical outcome on Days 2 through 5, TOC, and Follow-up Visits Sponsor-determined clinical outcome on Days 2 through 5; sponsor-determined clinical outcome and response at the TOC and Follow-up Visits

 To assess the relapse rate (microbiological and clinical) of acute cystitis after treatment with gepotidacin in adult female participants with acute cystitis at the Follow-up Visit 	
 Therapeutic response (combined per-participant microbiological and clinical response) at the Follow-up Visit

[figure not shown]
Objectives	Endpoints

To explore the microbiological and antimicrobial susceptibility profile of uropathogens recovered from adult female participants with acute cystitis, including subsets of isolates resistant to other antimicrobials	
Gram stain, quantitative bacteriology culture, and in vitro antimicrobial susceptibility test results at Baseline, Days 2 through 5, TOC, and Follow-up Visits

To explore gepotidacin plasma PK/pharmacodynamic (PD) relationships in adult female participants with acute cystitis	
Relationship between gepotidacin exposure and clinical and microbiological response, if data permit

To explore the distribution of gepotidacin in cervical, rectal, and pharyngeal tissue (swab specimens)	
Gepotidacin concentration in cervical, rectal, and pharyngeal tissues, if data permit

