10.3.3. Exploratory Analyses

Endpoint	Statistical Analysis Methods
Exploratory	
 Therapeutic response (number and percentage of participants with combined per-participant microbiological and clinical response) will be summarized by pathogen at the TOC Visit for the micro-ITT Population. The microbiological outcome and response (number and percentage of participants with microbiological success) will be summarized by pathogen group on Days 2 through 5 (outcome only) and at the TOC and Follow-up Visits for the micro-ITT Population. The clinical outcome and response (number and percentage of participants with resolution of signs and symptoms) will be summarized by pathogen group on Days 2 through 5 (outcome only) and at the TOC and Follow-up Visits for the micro-ITT Population. Therapeutic response (number and percentage of participants with combined per-participant microbiological and clinical response) at the Follow-up Visit for the micro-ITT Population. Gram stain, quantitative bacteriology culture, and in vitro antibacterial susceptibility testing results for urine specimens will be summarized at the Baseline Visit (predose on Day 1), on Days 2 through 5, and at the TOC and Follow-up Visits for the micro-ITT Population. The PK/PD relationship between gepotidacin exposure and microbiological and clinical outcome and/or response at the On-Therapy, TOC, and Follow-up Visits may be explored, if data permit. This may include assessment of gepotidacin exposures correlated with baseline minimum inhibitory concentrations and/or decreases in the baseline pathogen CFU/mL. Gepotidacin concentrations in cervical, rectal, and pharyngeal tissues will be summarized, if data permit.

The PK/PD exploratory analyses will be described in the RAP and may be presented separately from the main clinical study report.

Stool, vaginal, and pharyngeal microbiome specimens may be analyzed to assess the number and proportion of relevant bacterial populations and metabolomics, as data permit. This analysis may be presented separately from the main clinical study report.

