- The investigator- and sponsor-determined clinical outcome and response will be summarized for qualifying uropathogens isolated at baseline at the On-therapy, TOC, and Follow-up visits using counts and percentages. A participant will be counted multiple times under an uropathogen category if multiple qualifying uropathogens within that uropathogen category are isolated at baseline for the participant. In addition, participant level of clinical outcome will be summarized in the same table. The 95% Clopper-Pearson CI will be presented for the proportion clinical response at each visit.

- Clinical cure will be summarized for qualifying uropathogens isolated at baseline at the On-therapy, TOC, and Follow-up visits using counts and percentages.
A participant will be counted multiple times under an uropathogen category if multiple qualifying uropathogens within that uropathogen category are isolated at baseline for the participant. The 95% Clopper-Pearson CI will be presented for the proportion clinical cure at each visit.
- Percent of clinical cure and microbiological eradication over time will be plotted.
A participant with multiple qualifying uropathogens within an uropathogen category will be counted multiple times.
- The mean clinical symptom scores and boxplots of total score over time will be overlaid within one figure for the ITT population.

Table 7 Sponsor-Determined Clinical Outcome and Response

Defining Criteria	Outcome	Response
On-Therapy visit (Days 2 through 5 only)		

 • Resolution of or improvement in signs and symptoms of acute cystitis present at Baseline (and no new signs and symptoms) • Improvement is based on investigator-evaluated score and is defined as no increase of scores in each sign and symptom of acute cystitis present at Baseline and no new signs and symptoms of acute cystitis and no use of other antimicrobial therapy for the current infection 	
 • Clinical success 	
 • Not applicable

 • Increase of scores in any of signs and symptoms of acute cystitis present at Baseline or new signs and symptoms of acute cystitis or use of other antimicrobial therapy for the current infection 	
 • Clinical failure 	
 • Not applicable

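### SAP 2.2 sets time to eradication and time to resolution as exploratory objectives, but no time is derived for either, and daily percentages do not fix one when status can reverse

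*SAP*

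**What the plan says.** SAP 2.2 and Protocol Section 4 carry the same two objectives. For microbiology it is "To assess time to eradication of uropathogens in adult female participants with acute cystitis who have a qualifying baseline uropathogen", and the endpoint set against it is "Microbiological outcome on Days 2 through 5; Microbiological outcome and response at the TOC and Follow-up Visits". For symptoms it is "To explore time to resolution of signs and symptoms in adult female participants with acute cystitis". The SAP sets two endpoints against that, the first being "Investigator-determined clinical outcome on Days 2 through 5, TOC, and Follow-up Visits" and the second the sponsor-determined counterpart.

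The planned analyses follow the endpoints. Protocol 10.3.3 says "The microbiological outcome and response (number and percentage of participants with microbiological success) will be summarized by pathogen group on Days 2 through 5". SAP 9.1.1.3 says "Clinical cure will be summarized for qualifying uropathogens isolated at baseline at the On-therapy, TOC, and Follow-up visits using counts and percentages". The display closest to the objectives is described there as "Percent of clinical cure and microbiological eradication over time will be plotted", with the rule "A participant with multiple qualifying uropathogens within an uropathogen category will be counted multiple times".

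The list of displays (SAP 12.9.5 and 12.9.6, Tables 2.1 to 2.9 and Figures 2.1 to 2.3) also includes symptom scores and colony counts by visit. SAP Table 1, which records departures from the protocol, does not say that either time objective was dropped.

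**The concern.** A time objective needs an event definition (first or sustained), a unit that is counted once, a rule for missed assessments and other antibacterial use, and an estimate such as the cumulative proportion reaching the event by each day. None of these is given for efficacy. The only time-to derivation in the SAP concerns adverse event onset (12.5.2.1).

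The trial takes a culture and a symptom score on each of Days 2 to 5. As planned, the report could give the percentage clear on each day, but not the proportion that had cleared by that day or stayed clear from it.

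The resolution objective has a second gap. SAP Table 7 counts a participant as an on-therapy clinical success if no symptom score has risen from Baseline. A participant whose symptoms have not changed at all is therefore a success. Clinical cure (SAP Table 8) requires complete resolution, but SAP 2.2 does not list it against the objective.

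**Working it through.** The plan states no figure for either time, so there is none to reproduce. The question is whether the planned daily percentages determine a time.

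**Can status reverse?** Yes. SAP Table 5 has a recurrence category at TOC for a pathogen that was eradicated on therapy and then grows. Within Days 2 to 5, SAP Table 4 labels any growth at or above 10^3 CFU/mL as persistence, so regrowth after clearance has the same label as never having cleared.

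**Worked example.** Assumed data, because the micro-ITT size is not stated: 10 participants, one pathogen each, no missing cultures, with 4, 4, 6 and 8 eradicated on Days 2, 3, 4 and 5.

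- *Pattern A, no regrowth.* 4 are clear from Day 2, 2 from Day 4, 2 from Day 5, and 2 never clear.
- *Pattern B, with regrowth* (1 = clear, 0 = growth, in the order Days 2, 3, 4, 5). Two participants each have 1011, 1001, 0111, 0110 and 0001. Daily totals are 2+2 = 4, 2+2 = 4, 2+2+2 = 6 and 2+2+2+2 = 8, the same as in A.

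| Out of 10 | Day 2 | Day 3 | Day 4 | Day 5 | Median |
|---|---|---|---|---|---|
| Eradicated that day (A and B) | 4 | 4 | 6 | 8 | not defined |
| A: first eradicated by that day | 4 | 4 | 6 | 8 | Day 4 |
| A: sustained from that day or earlier | 4 | 4 | 6 | 8 | Day 4 |
| B: first eradicated by that day | 4 | 8 | 8 | 10 | Day 3 |
| B: sustained from that day or earlier | 0 | 2 | 4 | 8 | Day 5 |

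**General limits for the same percentages.** Write p2 to p5 for the daily proportions.

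- Eradicated at least once by Day 3 lies between max(p2, p3) = 0.4 and min(1, p2 + p3) = 0.8, that is 40% to 80%.
- Eradicated on every day from Day 2 lies between max(0, p2 + p3 + p4 + p5 − 3) = max(0, 2.2 − 3) = 0 and min(p2, p3, p4, p5) = 0.4, that is 0% to 40%.

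The planned plot would look the same across these ranges.

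**Is there a once-per-participant summary on Days 2 to 5?** For clinical outcome, yes (SAP 9.1.1.3). For microbiology, no: the participant-level summary is of response, which is defined only at TOC and Follow-up (SAP Tables 4 to 6). Clinical cure is described only by uropathogen.

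**The case against.** The best defence is that the endpoints are stated, the analysis follows them, and these are exploratory objectives in a single-arm PK study with no hypothesis test and a sample size based on feasibility. The sponsor also added daily clinical cure in order to look at complete resolution. If no one regrows and no culture is missed, the daily percentages equal the cumulative proportions and a median day can be read from the plot. This stands as a limit on importance. It does not close the gap, since the plan neither states nor checks that condition.

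It can also be said that the text of Protocol 9.1.3 describes on-therapy success as resolution. Table 6 in that section, and SAP Table 7, nevertheless admit symptoms that have merely not worsened.

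Three stronger readings are tempting, and the documents do not support them.

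- *Multiple counting is why the times are missing.* It applies only to a participant with two or more qualifying uropathogens in one category. It is a separate weakness of the by-uropathogen rows; counting everyone once would still give no time.
- *A missed on-therapy culture counts as not cleared.* With an assumed 12 participants that would cost up to 1/12 = 8.3 points per missed culture. But SAP Table 4 makes undetermined a category of its own on therapy, no denominator rule is stated, and participants are confined to the clinic through Day 5, so missed cultures should be few.
- *No time can be obtained at all.* Listings 12, 14 and 16 show outcomes and cultures by participant, so a reader could count first-clearance days by hand. What is missing is a prespecified definition and summary.

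**Conclusion.** The point holds as a mismatch between two exploratory objectives and what is planned for them. Neither time is derived, and daily status that can reverse fixes neither a time nor a cumulative proportion. In the example, identical daily percentages fit a median first eradication of Day 3 or Day 4 and a median sustained eradication of Day 4 or Day 5. Those figures rest on assumed data and an assumed regrowth pattern; with little regrowth the difference would be small. For resolution, the listed on-therapy outcome does not measure resolution whether or not status reverses.

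This is a worthwhile improvement rather than a serious defect. The primary PK analysis is unaffected.

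**What to change.** Add the following to the SAP, using data already collected:

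- For each micro-ITT participant, counted once, derive the first day on which all qualifying baseline uropathogens are below 10^3 CFU/mL, and the first day from which this holds at every later on-therapy culture.
- Derive the same two days for clinical cure (SAP Table 8) in the ITT population, because the resolution objective is not limited to participants with a qualifying uropathogen and display Table 2.9 already uses ITT. List clinical cure against that objective in SAP 2.2.
- Report the cumulative proportion by Days 2, 3, 4, 5 and TOC as the main output. With so few assessment times this is more informative than a median, which can follow as secondary (interval-censored or Kaplan-Meier) if estimable.
- From the start of another antibacterial, count the participant as not achieving the event. Censoring there would probably be informative, since a switch can follow lack of efficacy, and would conflict with the SAP rule that such use is not cure.
- Treat an isolated missed culture as interval-censored between the adjacent cultures.
- Keep the daily plots.

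The cost is two derived days per measure and one table. Estimates will be imprecise: 16 of 20, for example, is 80.0% with a 95% Clopper-Pearson interval of 56.3% to 94.3%. If the sponsor does not want a time estimate, rewording the objectives as the proportion eradicated or resolved on each day would remove the mismatch but leave the question of time unanswered.
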